NON-INTERVENTIONAL (NI) STUDY PROTOCOL

Study Information

Title	An Investigation of Tofacitinib PsA Initiators in the CorEvitas SpA Registry
Protocol number	A3921411
Protocol version identifier	3.0
Date	2 Oct 2023
Active substance	L04AA29
Medicinal product	Xeljanz® (tofacitinib IR/XR)
Research question and objectives	
The objectives of this study are as follows:
 
1. To describe the effectiveness of all tofacitinib initiators at 6 months in psoriatic arthritis (PsA) patients.2. To describe the effectiveness of all tofacitinib initiators at 6 months stratified by mono- and combination therapy of PsA.
Author	PPD [REDACTED], PhD, PPD [REDACTED], PPD [REDACTED] Pfizer Inc., [name] PPD [REDACTED]

This document contains confidential information belonging to Pfizer. Except as otherwise agreed to in writing, by accepting or reviewing this document, you agree to hold this information in confidence and not copy or disclose it to others (except where required by applicable law) or use it for unauthorized purposes. In the event of any actual or suspected breach of this obligation, Pfizer must be promptly notified.

2. LIST OF ABBREVIATIONS

Abbreviation	Definition
ACR	American College of Rheumatology
ACR 20/50/70	American College of Rheumatology 20/50/70
AE	adverse event
ANCOVA	Analysis of Covariance
AS	Ankylosing Spondylitis
bDMARD	biologic Disease Modifying Antirheumatic Drug
BSA	Body Surface Area
CABG	Coronary Artery Bypass Grafting
CHF	Congestive Heart Failure
CI	Confidence Interval
CRP	C-reactive Protein
csDMARD	Conventional Synthetic Disease Modifying Antirheumatic Drug
CV	cardiovascular
DAPSA	Disease Activity in Psoriatic Arthritis
DMARD	Disease Modifying Antirheumatic Drug
EQ-5D-5L	European Quality of Life Five Dimension Five Level
FDA	Food and Drug Administration
HAQ	Health Assessment Questionnaire
HAQ-DI	Health Assessment Questionnaire Disability Index
HAQ-S	Health Assessment Questionnaire Spine Flexibility

Abbreviation	Definition
HEOR	Health Economics and Outcomes Research
IEC	Independent Ethics Committee
IRB	Institutional Review Board
JAK	Janus Kinase
mACR 20/50/70	Modified American College of Rheumatology 20/50/70
MDA	Minimal Disease Activity
MI	Myocardial Infarction
PASDAS	PsA Disease Activity Score
PASS	Post Authorization Safety Study
PCI	Percutaneous Coronary Intervention
PsA	Psoriatic Arthritis
PsO	Psoriasis
SAP	Statistical Analysis Plan
SM	Small Molecule
SpA	Spondyloarthritis
SPARCC	Spondyloarthritis Research Consortium of Canada Enthesitis Index
TIA	Transient Ischemic Attack
TNF α	tumor necrosis factor inhibitor
tsDMARD	targeted synthetic Disease Modifying Antirheumatic Drug
US	United States

Abbreviation	Definition
VAS	Visual Analogue Scale
WPAI	Work Productivity Index

4. ABSTRACT

Not applicable.

5. AMENDMENTS AND UPDATES

Amendment number	Date	Protocol section(s) changed	Summary of amendment(s)	Reason
1	24May2023	9.3	Administrative change regarding CDAI and cDAPSA values	The values for CDAI and cDAPSA are being pulled from the database. Pfizer will not do any recalculation post-hoc
1	24May2023	9.5	Planned sample size reduced from 100 to 80 patients per group Substantial Amendment	Based on CorEvitas estimates and current enrollment pattern, it is estimated that it will take approximately 12 months to get to at least 80 patients per group.
1	24 May 2023	3	Adding Author (PPD) address and new PPD PPD	NY Pfizer offices changed
1	24 May 2023	6	Interim report 3, end of data collection, and final study report dates were updated	Update due to the amendment
2	02Oct2023	9.5	Planned sample size reduced from 80 to 73 patients per group Substantial Amendment	Based on CorEvitas estimates and current enrollment pattern, it is estimated that it will take approximately 12 months to get to at least 73 patients per group.

6. MILESTONES

Milestone	Planned date*
Start of data collection	15 November 2021
Interim Report 1	15 January 2022
Interim Report 2	19 December 2022
Interim Report 3	15 Sep 2023
End of data collection	29 March 2024
Final study report	28 June 2024

*The interim reports rely on reaching the appropriate number of patients for each analysis. These dates may change if there are delays in patient accrual within the registry.

7. RATIONALE AND BACKGROUND

Psoriatic arthritis (PsA) is an immune-mediated systemic inflammatory disease with multiple disease manifestations, including peripheral arthritis, enthesitis, dactylitis, and spondylitis, together with skin and nail psoriasis.¹ PsA may be associated with poor long-term outcomes and significantly diminished quality of life for patients.² PsA affects men and women equally with peak onset in adults between 30 to 50 years of age.³ Prevalence estimates in the US range from 0.06% to 0.25%.⁴ The incidence of PsA, ranges from 3.6 to 7.2 per 100,000 person-years.⁴ PsA is reported to occur in up to 30% of patients with PsO.⁵ Skin manifestations precede the PsA in 70% of patients.

According to evidence-based treatment recommendations by the Group for Research and Assessment of Psoriasis and Psoriatic Arthritis and the American College of Rheumatology (ACR), non-steroidal anti-inflammatory drugs and conventional synthetic disease-modifying antirheumatic drugs (csDMARDs) should be used in the early treatment of PsA. For patients in whom these are unsuccessful, biologic DMARDs (bDMARDs), such as tumor necrosis factor inhibitors, and targeted synthetic DMARDs (tsDMARDs), such as phosphodiesterase inhibitors are recommended.¹⁻⁶

Tofacitinib is an oral Janus kinase (JAK) inhibitor approved in 2017 by the US Food and Drug Administration (FDA) for the treatment of adult patients with active PsA who have had an inadequate response or intolerance to methotrexate or other DMARDs. Tofacitinib is approved for use in combination with nonbiologic disease modifying antirheumatic drugs (DMARDs) in psoriatic arthritis. Since approval, little is known about the patient profile of the PsA population treated with tofacitinib in clinical practice as well as the real-world effectiveness of tofacitinib in patients with psoriatic arthritis.

The purpose of this study is to provide a characterization of patients and effectiveness of tofacitinib in PsA patients newly initiating tofacitinib in the US CorEvitas PsA/spondyloarthritis (SpA) Registry. This study is not designed as a post authorization safety study (PASS) and is not a commitment or requirement to any regulatory authority.

8. RESEARCH QUESTION AND OBJECTIVES

There are two primary objectives for this study:

1. To describe the effectiveness of all tofacitinib initiators at 6 months in PsA patients.
2. To describe the effectiveness of all tofacitinib initiators at 6 months stratified by mono- and combination therapy of PsA.

9. RESEARCH METHODS

9.1. Study Design

To meet the study objectives, an observational retrospective cohort study will be conducted using patients enrolled in the CorEvitas PsA/SpA Registry initiating tofacitinib on or after 14 December 2017. Patients receiving tofacitinib will be included to assess the effectiveness of tofacitinib overall and stratified by key variables of interest. For further details, please refer to the detailed Statistical Analysis Plan (SAP) included as a stand-alone document.

9.2. Setting

The CorEvitas SpA Registry is a prospective, multicenter, observational disease-based registry launched in March 1st, 2013. This registry contains clinical data (eg, disease activity scores, laboratory results, comorbidities, imaging results, patient-reported outcomes data, etc.) that is not available in claims databases. As of August 1, 2020, the CorEvitas dataset includes 64 private and academic active clinical sites with over 66 providers throughout 30 states in the US. This registry collects data from both the providers and the patients at the time of a regularly-scheduled office visit. CorEvitas has enrolled over 4,000 patients with PsA or spondyloarthritis. The collection of data from CorEvitas represents over 9,800 patient years of data.

To be included in the CorEvitas PsA/SpA Registry, patients must be at least 18 years of age and have a diagnosis of PsA or AS by a rheumatologist. Patients are excluded from the registry if they are unable or unwilling to provide informed consent. The inclusion/exclusion criteria for this particular analysis are described in [Section 9.2.1](#) and [Section 9.2.2](#).

9.2.1. Inclusion Criteria

Patients must meet all of the following inclusion criteria to be eligible for inclusion in the study:

1. PsA patients in CorEvitas initiating tofacitinib monotherapy or in combination with oral small molecules (eg methotrexate, leflunomide, sulfasalazine, apremilast) after 14 December 2017 (market approval of tofacitinib in the US) with no prior use of tofacitinib. Only the patient's first initiation after December 14, 2017 will be included in the analysis.
2. Have a 6 month follow-up visit (with ± 3 month window).

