9.5. Study Size

This is an estimation study and not hypothesis testing study. Precision estimates indicate that approximately 80-73 patients with 12 months of follow-up are needed per group to achieve reasonably precise estimates for the outcomes of interest. For binomial proportions, a sample size of 80-73 patients per group would yield a half width of the 2-sided 95% confidence interval (CI) to be less than 11 percentage points for the binomial proportions, and less than 16 percentage points for the difference in 2 binomial proportions.

As of October 1, 2020, there are 160 tofacitinib initiators within the CorEvitas registry of whom 93 have a 6 month follow-up visit. The first objective of the study will be assessed using the latest data cut available once the protocol is approved and will be reported in the first interim report. The stratifications by mono and combination therapy listed in the second objective will be reported in subsequent interim reports as sample sizes reach appropriate thresholds. For comparative analyses, this will be at least 80-73 patients per arm. Precision estimates will be used to determine appropriate sample sizes for the descriptive analyses. The final report will be issued once all subgroups reach the minimal sample sizes to ensure sufficient precision in the estimates of the outcomes.

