**Title: Analysis of tofacitinib initiators with PsA**

**Overall Aim:** To describe baseline demographic, therapy history, and disease activity characteristics and assess change in disease activity measures six months after initiation of tofacitinib

To accomplish the overall aim, we will:

**Objective 1:** Summarize patient characteristics at baseline and calculate changes in various disease activity measures over time among all eligible initiators of tofacitinib

**Objective 2:** Summarize patient characteristics at baseline and calculate changes in various disease activity measures separately for monotherapy and combination therapy initiators, and compare these groups

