#### **Study Cohort:**

For this analysis, the eligible population will be selected using the following criteria:

- Have a diagnosis of PsA
- Initiate tofacitinib monotherapy or in combination with OSMs (pre-existing or concurrent) during or after December 2017
- Have a follow-up visit occurring six ( $\pm 3$ ) months after initiation

Initiators will be ineligible for analysis if:

Any initiations result in a combination of tofacitinib with TNFi or non-TNFi bDMARDs, whether multiple initiations occur at the same time or a new therapy is added to an existing regimen

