**Feasibility Assessment and Projections:**

Using the October 1, 2021 version of the PsA registry, we have identified the following therapy patterns among initiators of tofacitinib

	Eligible Initiations, N (%)
All tofacitinib initiations	213
Monotherapy	132 (62.0)
Combination with OSMs only	81 (38.0)
Combination with MTX	58 (71.6)

	Monotherapy	Combination with OSMs
Eligible Initiators	132	81
Six-month visit	59 (44.7%)	55 (67.9%)

**Shell Tables****Table 1.** Patient demographic characteristics among all tofacitinib initiators

All Patients, N	Overall
Age (years), n, Mean (SD), [P0,P25,P50,P75,P100]	
Female, n/N (%)	
Race, n/N (%)	
White	
Black	
Asian	
Other	
Work Status, n/N (%)	
Full Time/Part Time	
Retired	
Disabled	
Other	
BMI (kg/m  ), n, Mean (SD), [P0,P25,P50,P75,P100]	
BMI Category (kg/m  ), n/N (%)	
< 25	
25 to < 30	
30 +	
Duration of PsA Symptoms (years), n, Mean (SD), [P0,P25,P50,P75,P100]	
Time Since PsA Diagnosis (years), n, Mean (SD), [P0,P25,P50,P75,P100]	

All Patients, N	Overall
Time Since PsO Onset (years), n, Mean (SD), [P0,P25,P50,P75,P100]	
Psoriasis, n/N (%)	
Psoriatic Nail Dystrophy, n/N (%)	
History of Comorbidities, n/N (%)	
CVD b	
Depression	
Diabetes	
Malignancy c	
NMSC	
Hypertension	
Hyperlipidemia	
Crohns Disease	
Anxiety	
Fibromyalgia	
Serious Infections d	
Metabolic Syndrome	
Ulcerative Colitis	
Uveitis	
Smoking Status, n/N (%)	
Never	
Previous	
Current	
Cigarettes per day, n, Mean (SD), [P0,P25,P50,P75,P100]	
Smoking duration, n, Mean (SD), [P0,P25,P50,P75,P100]	
Alcohol Use, n/N (%)	
Number drinks per week, n, Mean (SD), [P0,P25,P50,P75,P100]	
Prior Biologics, n, Mean (SD), [P0,P25,P50,P75,P100]	
Number of Prior Biologics, n/N (%)	
0	
1	
2 +	
Prior TNFs, n, Mean (SD), [P0,P25,P50,P75,P100]	
Number of Prior TNFs, n/N (%)	
0	
1	
2 +	
Prior non-TNFs, n, Mean (SD), [P0,P25,P50,P75,P100]	
Number of Prior non-TNFs, n/N (%)	

All Patients, N	Overall
0	
1	
2 +	
Prior OSMs, n, Mean (SD), [P0,P25,P50,P75,P100]	
Number of Prior OSMs, n/N (%)	
0	
1	
2 +	
Current OSM Use, n/N (%)	
Current MTX Use, n/N (%)	
Current NSAID Use, n/N (%)	
Current Opioid Use, n/N (%)	
Current Aspirin Use, n/N (%)	
Prednisone Use, n/N (%)	
None	
Missing Dose	
Dose < 10 mg	
Dose $\geq$ 10 mg	
Tender Joints (28), n, Mean (SD), [P0,P25,P50,P75,P100]	
Tender Joints (68), n, Mean (SD), [P0,P25,P50,P75,P100]	
Swollen Joints (28), n, Mean (SD), [P0,P25,P50,P75,P100]	

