b History of cardiovascular disease includes history of: hypertension, hyperlipidemia, cardiac revascularization procedure (CABG, stent, angioplasty), ventricular arrhythmia, cardiac arrest, myocardial infarction, acute coronary syndrome, unstable angina, CHF (with and without hospitalization), stroke, transient ischemic attack, other CV, deep vein thrombosis, peripheral arterial disease, peripheral arterial thrombosis, urgent peripheral revascularization, peripheral ischemia/gangrene, pulmonary embolism, carotid artery disease, and hemorrhage.

c Malignancy includes breast cancer, lung cancer, lymphoma, skin cancer (squamous cell), and other cancers.

d Serious infections include the following: joint/bursa infection, cellulitis, sinusitis, diverticulitis, sepsis, pneumonia, bronchitis, gastroenteritis, meningitis, urinary tract infection, upper respiratory infection, tuberculosis, and other infections.

e Biologics: Humira, Enbrel, Cimzia, Simponi, Remicade, Orencia, Taltz, Cosentyx, Stelara

f TNFs: Humira, Enbrel, Cimzia, Simponi, Remicade

g non-TNFs: Orencia, Taltz, Cosentyx, Stelara

h cDMARDs: MTX, Arava, Azulfidine, Otezla

i Clinical Global Assessment of PsO is scored on a five-point scale from 0-4, with corresponding interpretations of Clear, Almost Clear, Mild, Moderate, and Severe, respectively.

**Table 2.** Therapy status six months post-initiation

All Patients, N	Overall
Remain on tofacitinib, n (%)	
Discontinued tofacitinib, n (%) a	
Switched to a bDMARD, n (%) b	

a This group consists of those discontinuing tofacitinib and not initiating a bDMARD at or prior to the six-month follow-up visit

b This group consists of those discontinuing tofacitinib and initiating a bDMARD at or prior to the six-month follow-up visit

**Table 3.** Summary statistics of continuous outcomes at baseline, six months, and change from baseline to six months

All Initiators, N	Overall
Achievement of:	Response Rate (95% CI)
LDA (cDAPSA)	
Minimal Disease Activity	
Body Surface Area Score of 0	
PASDAS < 3.2	
Resolution of enthesitis	
Resolution of dactylitis	
Clinical Global Assessment of PsO – Clear or Almost Clear	

		Overall
		n, mean (SD), [P0,P25,P50,P75,P100]
cDAPSA	Baseline	
	Six Months	
	Difference a	
DAPSA	Baseline	
	Six Months	
	Difference a	
PASDAS	Baseline	
	Six Months	
	Difference a	

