HAQ-DI	Baseline	
	Six Months	
	Difference a	
BSA	Baseline	
	Six Months	
	Difference a	
CDAI	Baseline	
	Six Months	
	Difference a	
Tender joint count (68)	Baseline	
	Six Months	
	Difference a	
Swollen joint count (66)	Baseline	
	Six Months	
	Difference a	
Patient global skin assessment	Baseline	
	Six Months	
	Difference a	
Patient pain	Baseline	
	Six Months	
	Difference a	
Patient fatigue	Baseline	
	Six Months	
	Difference a	

		Overall
Clinical Global Assessment of PsO	Baseline	
	Six Months	
	Difference a	
Work time missed	Baseline	
	Six Months	
	Difference a	
Impairment while working	Baseline	
	Six Months	
	Difference a	
Overall work impairment	Baseline	
	Six Months	
	Difference a	
Activity impairment	Baseline	
	Six Months	
	Difference a	

a Calculated as six-month value minus baseline value

**Table 4.** Patient demographic characteristics by monotherapy and combination therapy, among all tofacitinib initiators

	Overall	Mono	Combo	p-value
All Patients, N				
Age (years), n, Mean (SD), [P0,P25,P50,P75,P100]				
Female, n/N (%)				
Race, n/N (%)				
White				
Black				
Asian				
Other				
Work Status, n/N (%)				
Full Time/Part Time				
Retired				
Disabled				
Other				
BMI (kg/m  ), n, Mean (SD), [P0,P25,P50,P75,P100]				
BMI Category (kg/m  ), n/N (%)				
< 25				
25 to < 30				
30 +				
Duration of PsA Symptoms (years), n, Mean (SD), [P0,P25,P50,P75,P100]				
Time Since PsA Diagnosis (years), n, Mean (SD), [P0,P25,P50,P75,P100]				
Time Since PsO Onset (years), n, Mean (SD), [P0,P25,P50,P75,P100]				
Psoriasis, n/N (%)				
Psoriatic Nail Dystrophy, n/N (%)				
History of Comorbidities, n/N (%)				
CVD b				
Depression				
Diabetes				
Malignancy c				
NMSC				
Hypertension				
Hyperlipidemia				
Crohns Disease				
Anxiety				
Fibromyalgia				
Serious Infections d				
Metabolic Syndrome				

	Overall	Mono	Combo	p-value
Ulcerative Colitis				
Uveitis				
Smoking Status, n/N (%)				
Never				
Previous				
Current				
Cigarettes per day, n, Mean (SD), [P0,P25,P50,P75,P100]				
Smoking Duration, n, Mean (SD), [P0,P25,P50,P75,P100]				
Alcohol Use, n/N (%)				
Number drinks per week, n, Mean (SD), [P0,P25,P50,P75,P100]				
Prior Biologics, n, Mean (SD), [P0,P25,P50,P75,P100]				

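### The objectives cover all tofacitinib initiators, but entry requires a visit 6 (±3) months after initiation, and no outcome analysis in the available text covers initiators without one

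*Protocol*

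**What the plan says.** Protocol section 8 gives the first objective as "To describe the effectiveness of all tofacitinib initiators at 6 months in PsA patients". The second objective is the same, stratified by monotherapy and combination therapy.

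Protocol section 9.2.1 requires every inclusion criterion to be met. The second criterion is "Have a 6 month follow-up visit (with ± 3 month window". The SAP Study Cohort carries the same condition, "Have a follow-up visit occurring six" (±3) months after initiation. SAP Objective 1 is to "calculate changes in various disease activity measures over time among all eligible initiators of tofacitinib".

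The SAP does not use 'eligible' in one sense. Under Study Cohort the visit is part of eligibility. Under Feasibility Assessment and Projections, 132 monotherapy and 81 combination patients are labelled eligible initiators, and the visit is applied only in the next row (59 and 55). The table labels do not settle the population either. Table 1 is titled "Patient demographic characteristics among all tofacitinib initiators" and Table 4 "Patient demographic characteristics by monotherapy and combination therapy, among all tofacitinib initiators", while Tables 3 and 7 are headed as covering all initiators.

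Under Milestone 2, binary outcomes are set to non-response when the value is missing or the patient stopped therapy before follow-up. Milestone 1 states no such rule. Tables 2 and 5 classify therapy status relative to the six-month visit. Their discontinued row, for example, holds "those discontinuing tofacitinib and not initiating a bDMARD at or prior to the six-month follow-up visit". Neither table has a row for patients without that visit.

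**The concern.** Whether a patient returns between 3 and 9 months is known only after treatment has started, and it may depend on how treatment went. Protocol section 9.9 says that visits follow no fixed schedule. Section 9.4 says that starting a different eligible drug prompts an extra visit. Selection by attendance is therefore plausible, and it could act in either direction.

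The response rates in Tables 3 and 6 would describe initiators who came back in the window, while the protocol objectives name all initiators. Nothing in the available text counts the patients whose window closed without a visit, compares them with the others, or bounds their effect. A reader could not tell how far the reported rates apply to the population that the objectives name.

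**Working it through.** **1. The plan's own feasibility figures (SAP, 1 October 2021).**
- Initiators: 132 + 81 = 213.
- With a six-month visit: 59/132 = 44.7% on monotherapy and 55/81 = 67.9% on combination therapy, as printed. In total 59 + 55 = 114.

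**2. Without a visit at that date.**
- Monotherapy: 132 − 59 = 73.
- Combination: 81 − 55 = 26.
- Total: 73 + 26 = 99, and 99/213 = 46.5%.

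The window closes 9 months after initiation, so anyone who started after 1 January 2021 could still have had a visit. The SAP does not split the 99 into open and closed windows. Protocol section 6 runs data collection to 29 March 2024. The 46.5% is therefore a snapshot and not the share that will finally be excluded.

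**3. An illustration for closed windows.** Protocol section 9.5 says that at 1 October 2020 "there are 160 tofacitinib initiators within the CorEvitas registry of whom 93 have a 6 month follow-up visit". Every one of those windows had closed by 1 July 2021, before the second count. Assume that both counts use the same eligibility basis and visit definition, that all 160 are among the 213, and that a visit counted in 2020 still counts in 2021. Then:
- Later starters: 213 − 160 = 53.
- Fewest of the 160 without a visit, if all 53 later starters are among the 99: 99 − 53 = 46, and 46/160 = 28.8%.
- Most of the 160 without a visit, if none of those lacking one in 2020 gained one: 160 − 93 = 67, and 67/160 = 41.9%.
- Cross-check on the lower figure: visits rose by 114 − 93 = 21, and 67 − 21 = 46.

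Section 9.5 does not state its eligibility basis. If some of the 160 would not count among the 213, the lower figure falls. The range is illustrative only.

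**4. Does the non-response rule reach these patients?** Under the Study Cohort definition, a patient without an in-window visit is removed before any rule on missing values applies. A patient who attends with a missing score counts as a non-responder in Table 6. A patient who does not return in the window is not counted at all, even after stopping therapy. If 'eligible' were read as in the feasibility table, the rule could be taken to reach such patients, but the cohort definition does not support that reading.

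**5. Other tables.** Read by their titles, Tables 1 and 4 might describe these patients at baseline. Tables 2 and 5 have no place for them. Tables 3, 6 and 7 report outcomes at the six-month visit.

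**The case against.** A fair defence has four parts.

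- **The word 'all' may only separate objective 1 from the stratified objective 2.** Section 9.2.1 defines the study population openly, section 9.9 admits limited representativeness and the use of visit windows, and both documents print visit counts. It stands that nothing is hidden and that a visit-only cohort can be kept. Disclosing the rule still does not report or bound the exclusion at the final data cut.
- **The size is poorly known.** This stands. The only directly documented figure is 99 of 213, open windows included.
- **Lack of an in-window visit is not evidence of non-response when visits follow no fixed schedule.** This stands as a limit on interpretation. A non-responder analysis is legitimate only if it is labelled a conservative bound.
- **Protocol section 9.9 breaks off within its missing-data text.** Something relevant may sit there, so nothing is inferred from it.

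A reader might also infer that monotherapy patients are lost more often (73/132 = 55.3% against 26/81 = 32.1%) and that the group comparison is therefore biased. The documents do not support this. The share of open windows in each group is not given, so the gap may partly reflect recent starts.

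**Conclusion.** The point holds. The protocol objectives name all initiators, while both cohort definitions admit only those with a later visit. Under the SAP Study Cohort, no outcome analysis in the available text covers the rest. The SAP's two uses of 'eligible' leave the denominators of several tables unclear.

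On size, 99 of 213 (46.5%) lacked a visit in the October 2021 snapshot, with open and closed windows mixed. The figure of 46 to 67 of 160 for closed windows rests on the two counts being comparable, which the documents do not say.

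A reader might infer that nearly half of initiators will be excluded, or that the reported response rates will be too high. Neither follows: the final share is not established, and the direction of any bias is unknown. The visit-only analysis can run as planned. This is a cheap improvement in what its results can be said to represent.

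Separate and minor: the non-response and discontinuation rule appears only under Milestone 2, so a patient who stopped therapy could count as a responder in Table 3 and a non-responder in Table 6.

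**What to change.** Keep the visit-only analysis and its per-group thresholds. Then:

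- Use 'eligible' in one sense across SAP Objective 1, Study Cohort and the feasibility table, and state the population of Tables 1, 3, 4 and 7.
- Define in the protocol and SAP a second cohort: all otherwise eligible initiators with an index date at least 9 months before the data cut.
- In that cohort, add a row to Tables 2 and 5 for patients with no six-month visit, by therapy group. Separate those seen only outside the window from those with no later visit.
- In that cohort, compare baseline characteristics of patients with and without an in-window visit.
- In that cohort, add a supportive analysis of the binary outcomes that counts patients without an in-window visit as non-responders, labelled as a conservative bound. Give each outcome the same at-risk denominator as its main analysis. This matters because the SAP lists cDAPSA low disease activity outside the outcomes restricted to patients not already in the target state. A repeat using the nearest out-of-window visit is optional.
- As the separate minor point, apply the Milestone 2 non-response and discontinuation rule to the Table 3 response rates, and say so under Milestone 1.

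The cost is modest programming on data already in the registry. The supportive rates may be less favourable, and the out-of-window repeat would mix assessment times.
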